4.5.1 Description of the ODO function

Among the programmable pacing modes, the user can activate the ODO mode with the programmer device, by selecting "OFF" in the "Modes" window. During the ODO mode the pacemaker does not deliver any pacing therapy, while it maintains all the sensing and related diagnostic functions to monitor cardiac rhythm. In standard operating conditions, pacing OFF is a temporary function: it is active until the programming head is applied or the radiofrequency telemetry connection (SafeSync®) is enabled. The BIOSync CLS study design requires the pacing OFF condition (ODO mode) to be permanently active (without the programming head or radiofrequency connection) during the patient's participation in the study (that is until the first adjudicated syncope recurrence, follow-up termination or study withdrawal).

In order to activate the OFF mode permanently, a special code is required by the programmer software.

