6.3 Steps to control or mitigate the risks

As reported in the Risk Analysis and in the IB the following measures will be adopted to mitigate the risks associated with the participation in the study.

Clinical Investigation Plan and Study Design shall include:

- 1) An independent DSMB will be monitoring the study conduct reviewing all available source document related to any death occurring during the study and recommending early study termination, if deemed appropriate.
- 2) Should a patient in ODO mode study arm die, source document review will be performed immediately, without any undue delay as soon as all relevant documents are available
- 3) The following procedures have been introduced in the study CIP:
 - Subjects terminate study participation at the first adjudicated syncope recurrence
 - Three interim analysis are planned to early terminate the study in case of evidence of superiority of the treatment arm
 - independent DSMB to periodically monitor the study status and preliminary results, recommending termination in case of unacceptable risk
 - Investigators are allowed to take any medical decision deemed appropriate, including pacemaker reprogramming
 - Advice the patient to avoid activity which may pose risks in case of transient loss of consciousness
- 4) The password/code is communicate only to hospital staff involved in the study after appropriate training
- 5) Resuscitation equipment available during pacemaker setup
- 6) The following measures must be taken during a TT:
 - a pacemaker programmer available in the room and switched on before the test starts
 - Adherence to current guidelines
 - Use of nitroglycerine
 - Resuscitation equipment available during tests
- 7) Initial training and, if necessary, periodic re-training of the hospital study staff

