8.8.6 Point of enrolment and study termination

A subject is considered enrolled in the BIOSync CLS Study upon the signature of the Informed Consent Form.

Patients will terminate their study participation at the 24-month in-hospital follow-up or at the assessment of a primary endpoint event occurrence, whichever comes first.

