9.9 Primary and clinical secondary endpoint Adjudication Board

All the unclassified syncope or pre-syncope episodes (see section 8.3.3) will be adjudicated by an Adjudication Board of at least 3 members. The members will be selected among experienced physicians with documented expertise in syncope. The members will not participate in the study as Investigators

The Adjudication Board will review unclassified endpoint events according to a charter provided in a separate document.

The members will remain blinded to the randomization, even if they will have access to the electronic CRF.

The adjudication process will be requested by the study Project Manager after the required number of primary endpoint events for the interim analyses has exceeded the predefined levels (see section 11.6).

The interim analyses will be performed only with the events collected at the times of the call for the adjudication from the Project Manager. Further events possibly occurring thereafter will not be included.

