11.7.1 Stopping Rules

1. The CCI will be informed monthly by the CRO about the total number of patients who will experience a syncope recurrence (primary endpoint event).
2. When the number of events will reach¹ the predefined limits for interim analyses (40% and 70% of the expected number of events), open queries will be resolved and on site monitoring visits for source data verification will be performed.
3. Unclassified primary endpoint events will be adjudicated (see section 9.9). If available primary endpoint events will be less than the predefined limits for interim analyses after the adjudication process, endpoint point event collection will continue until the required number will be reached.
4. When data set will be cleaned the clinical project manager of the study will inform the appointed independent statistician.
5. The independent statistician will analyze the data according to the Statistical Analysis Plan (SAP). The results will be communicated to the CCI and the sponsor of the study. If the

¹ The number of events may exceed the programmed limit whenever 2 or more events occur at the same time.

primary objective is reached the study stops immediately. The stop date of the study is the date of insertion in the database of the last syncopal recurrence. If the primary objective is not reached the independent statistician will recommend to continue the study until 62 events will be collected. Investigators will not be informed of the results of the interim analyses.

6. After study closure investigators shall complete missing data (apart from the primary events) and close open queries within the following 2 months. Events occurring after the stop date shall not be considered either for primary or for secondary endpoints.

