7.5 Evaluation of study objectives

The BIOSync CLS study (BA103, CIP ver. 7.0) gathers primary and secondary endpoints' data through self-administered patient questionnaires. In order to ensure double-blinding in endpoint assessment, the questionnaires will be collected by external personnel of an appointed CRO. This process is descripted in detail in the Charter for patient questionnaire collection and adjudication, version 2.0, 06-Mar-2017, and summarized in the below image.

At the end of the adjudication the following derived variables will be created.

Variable name	List of values	Unit of measure	Description	
pe	0 (No); 1 (Yes)	*	Occurrence of syncope episode	
time_pe	Numeric	days	If pe=1: time to the first post	
			randomization recurrence of a	
			syncopal episode;	
			If pe=0: total follow-up time	
se	0 (No); 1 (Yes)	-	Occurrence of pre-syncope or	
			syncope episode	
time_pe	Numeric	days	If pe=1: time to the first post	
			randomization recurrence of a pre-	
			syncope or syncope episode	
			whichever comes first.;	
			If pe=0: total follow-up time	

The analysis of the primary and secondary study objectives will be performed with the following code (STATA language).

stset time_pe, failure(pe==1)

*Kaplan_meier plots generation

sts graph by(rd_display), ci risktable

*Comparison of survivors functions

sts test rd_display, logrank

*Proportional hazard Cox models for major baseline predictors

stcox rd display

estat phtest

stcox gi_age

stcox gi_gender

stcox hs syncop life

stcox hs_syncop_lastyear

stcox ecg_mean_hr

stcox tt_response

stcox tt_pause_max

stcox tt_pause_type

stcox tt_time_pre_sync

^{*}Study objectives evaluation

^{*}Primary endpoint

*Secondary endpoint

stset time_se, failure(se==1)

*Kaplan_meier plots generation
sts graph, by(rd_display) ci

*Comparison of survivors functions
sts test rd_display, logrank

*Proportional hazard Cox models for major baseline predictors
stcox rd_display
estat phtest
stcox gi_age
stcox gi_gender

stcox hs_syncop_lastyear stcox ecg_mean_hr

stcox tt_response stcox tt_pause_max

stcox hs_syncop_life

stcox tt_pause_type stcox tt_time_pre_sync

stcox tt_low_bp

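### Low-priority safety improvement: for syncopes the questionnaire leaves unclassified, the only stated trigger for Board review is the trial's interim event count, although the first adjudicated syncope is what ends ODO

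*Protocol*

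**What the plan says.** - **What ends ODO.** Protocol 4.5.1 keeps permanent ODO active during participation, "that is until the first adjudicated syncope recurrence, follow-up termination or study withdrawal". Section 6.3 lists among its risk mitigations: "Subjects terminate study participation at the first adjudicated syncope recurrence". Section 8.8.6 words the exit differently, as the 24-month visit or "at the assessment of a primary endpoint event occurrence, whichever comes first".
- **When the Board is called.** Protocol 9.9 sends all unclassified syncope and pre-syncope episodes to the Adjudication Board, under a separate charter. The only timing it states is: "The adjudication process will be requested by the study Project Manager after the required number of primary endpoint events" for the interim analyses has been passed. Section 11.7.1 steps 2 and 3 repeat this at 40% and 70% of the events, which 11.6 gives as 25 and 43. Neither document states a per-episode or calendar trigger.
- **What else protects the patient.** Under 8.3.3 the questionnaire responses determine whether an event fits an endpoint, and the CRO tells the investigator about syncope and pre-syncope. Section 6.3 adds: "Investigators are allowed to take any medical decision deemed appropriate, including pacemaker reprogramming". Under 9.6 a mode change is not a crossover if a primary endpoint justifies it, even when that is assessed afterwards.
- **What was not available.** SAP 7.5 refers for detail to the "Charter for patient questionnaire collection and adjudication, version 2.0" and to a process figure. We had neither.

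**The concern.** ODO is an off-label mode (4.5, 6.2.3), and leaving it after a confirmed recurrence is one of the listed safeguards. For an unclassified episode that safeguard has no patient-level timeline in the protocol. The Board is called when enough other patients have had events, and after the 43-event call no further call is stated before the final analysis. Until the Board rules, protection rests on the investigator choosing to reprogram without a ruling. What is at stake is a second syncope, in ODO, in a patient whose first was real but not yet classified. The efficacy analysis is not at stake: the endpoint in SAP 7.5 is the time to the first syncope, and a late ruling does not move that date.

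**Working it through.** **Reproducing the trigger counts.** The Schoenfeld form, with the log hazard ratio squared, gives (1.960 + 0.842)² / (0.25 × (ln 0.49)²) = 7.849 / 0.1272 = 61.7, so 62 events as in 11.2.1. Then 0.4 × 62 = 24.8 and 0.7 × 62 = 43.4, which are the plan's 25 and 43.

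**Inputs from protocol 11.2 and 8.3.3.** 128 patients randomized 1:1; 2-year incidence 57% (ODO) and 34% (paced); exponential times; 2-year accrual; 10% loss; 24-month follow-up; quarterly questionnaires.
- ODO hazard: −ln(0.43)/24 = 0.0352 per month.
- Paced hazard: −ln(0.66)/24 = 0.0173 per month.

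**Assumptions added.** Uniform accrual; loss read as 10% over 2 years; report at the next quarterly mailing plus 14 days; unclassified episodes counted toward 25 and 43, as 11.7.1 step 3 implies; a final Board round at month 48; no efficacy stop. The wait is simulated for all ODO first syncopes and taken to apply equally to the unclassified ones.

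**Wait from report (6,000 simulated trials, about 35 ODO first syncopes per trial).**

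| Quantity | Result |
|---|---|
| Reported before the 43-event call | 78% |
| Of these, median time to next Board call | 5.3 months |
| All ODO reports, median time to Board call | 6.4 months |
| All ODO reports, median time to earlier of call or own 24-month exit | 5.1 months |
| Own exit comes before the Board call | 30% |

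With efficacy stops simulated, the last three become 6.0 months, 5.1 months and 23%.

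**Sensitivity of the median time to the Board call, all reports** (a separate run of 4,000 trials, base case 6.3 months):
- no treatment effect: 4.3
- 12-month accrual: 4.8
- paced incidence 20%: 7.4
- 10% unclassified and not counted toward the trigger: 7.6
- 36-month accrual: 8.0
- incidences 40% and 24%: 9.5
- 30% unclassified and not counted: 10.4

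The range is therefore about 4 to 10 months. These waits start at the report; quarterly mailing can add up to about 3 months after the episode.

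**Avoidable second syncopes.** Let W be the wait to the earlier of call or own exit.
- Stay in ODO throughout: mean of 1 − exp(−0.0352 W) = 0.172.
- Monthly review, switched to pacing after about 0.5 month: mean of 1 − exp(−0.0352 × 0.5 − 0.0173 × (W − 0.5)) = 0.099, with the ODO part cut at W where W is shorter than 0.5.
- Difference: about 0.074 per unclassified ODO syncope later confirmed (0.073 to 0.074 between runs).

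Hand check at the median, W = 5.1: 1 − exp(−0.1795) = 0.164; 1 − exp(−0.0176 − 0.0796) = 0.093; difference 0.072.

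The documents do not give the unclassified share. Taking 10%, 25% and 50% of about 34.8 ODO syncopes:
- 0.074 × 34.8 × 0.10 = 0.26
- 0.074 × 34.8 × 0.25 = 0.64
- 0.074 × 34.8 × 0.50 = 1.29

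If half of these patients are reprogrammed on the CRO notice, the range is about 0.13 to 0.64.

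**The case against.** The strongest reply is that patient protection does not run through the Board. The CRO tells the investigator, who is not blinded and may reprogram at once, and 9.6 lets a later ruling justify the change. On this view the 9.9 trigger is event cleaning before an interim look. The detailed procedure is delegated to a charter, and its absence from our material is not a gap in the plan. The Board's members also form the DSMB (18.11), which 6.3 says monitors the study periodically.

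Most of this stands and is why the priority is low. It does not remove the point. Reprogramming is at the investigator's discretion, and someone acting before the ruling cannot know whether the change will later count as a crossover. The notice is also described unevenly: 8.3.3 covers syncope and pre-syncope, while Table 4 in 9.6 speaks of an adverse event. Neither 6.3 nor 18.11 gives the DSMB the task of ruling on unclassified episodes.

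Stronger readings a reader might infer are not supported:
- *Patients are held in ODO until the Board meets.* Section 6.3 allows reprogramming at any time.
- *Every ODO syncope waits about 5 months.* Only unclassified episodes go to the Board, and their number is unknown.
- *All second syncopes during the wait are avoidable.* That would mean no recurrence under pacing; the plan itself assumes 34% at 2 years, which roughly halves the avoidable number.

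**Conclusion.** The point holds as a cheap, low-priority safety improvement. For unclassified episodes, the interim event count is the only Board trigger that 9.9 and 11.7.1 state, although adjudication is the exit that 4.5.1 and 6.3 rely on. The modelled wait has a median of about 5 months to the earlier of call or own exit, and about 4 to 10 months to the call itself across sensitivity runs. The avoidable harm is about 0.3 to 1.3 syncopes in the whole trial if nobody reprograms, and about half that if half are reprogrammed. This rests on the plan's hazards continuing after a first recurrence, the 34% paced incidence applying after the switch, and an assumed 10% to 50% unclassified share. If the charter already provides earlier review, the practical gap closes and only the protocol wording remains. The difference between *adjudicated* (4.5.1, 6.3) and *assessment* (8.8.6) is a wording point; it does not show that two exit rules were intended.

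**What to change.** Amend protocol 9.9, and the charter if it does not already say so, so that unclassified episodes go to the existing blinded Board on a rolling basis. The monthly report in 11.7.1 step 1 ("The CCI will be informed monthly by the CRO about the total number of patients") is a natural occasion. Keep a final check of outstanding episodes before each interim look and before the final analysis. Use one term in 4.5.1, 6.3 and 8.8.6 for the event that ends ODO.

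The cost is wording plus more frequent, shorter Board reviews of the same caseload by the same members. Blinding, alpha, boundaries, event target and sample size do not change.

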9.10 Possible influencing factors on outcome or interpretation of results

No factors that could influence the outcome or interpretation of the results are known at time of protocol drafting.

10 MONITORING PLAN

The responsibility of BIOTRONIK as sponsor is to ensure protocol and regulatory compliance through proper monitoring of the study. BIOTRONIK is required to ensure that the investigational device is used under the immediate direction of an investigator. As the investigator, the physician is responsible for conducting the study in accordance with the signed clinical investigation agreement, the study protocol, applicable laws, and FDA and/or local regulations (e.g. CFR 21, parts 50, 54, 56, and 812, ISO 14155, Declaration of Helsinki) and any conditions of approval imposed by the reviewing IRB/EC.

The entries in the eCRF will be reviewed and source data verified at the investigational site by monitors (authorized BIOTRONIK personnel, Clinical Research Associates-CRAs, or by authorized BIOTRONIK designees) to ensure that the investigator and the clinical investigation team conducts the clinical investigation in accordance with the CIP, The Declaration of Helsinki, ISO 14155, and applicable FDA and local laws and regulations to ensure adequate protection of the rights, safety and wellbeing of subjects and the quality and integrity of the resulting data.

A monitor will visit the study site periodically during the study. All participating sites will be monitored during the course of the study with visits occurring as frequently as deemed necessary to ascertain adherence to the protocol procedures, as well as maintenance of the highest quality data. A detailed monitoring plan developed by BIOTRONIK will be followed.

Periodic monitoring visits will assure, amongst others, that the facilities are still acceptable; that the CIP is being followed, that the EC/IRB/CA has been informed about approved CIP changes as required, that records on study conduct and data collection are complete and present, that appropriate and timely reports have been made to the sponsor and the authorities, and that the investigator is carrying out all agreed activities.

Periodic monitoring visits, assessments of the study site will include but will not be limited to the following:

1. Availability and correctness of the signed patient informed consent
2. Completion and submission of the required case report forms and other applicable study documentation
3. Continued acceptability of the facilities
4. Adherence to the clinical investigation plan
5. Adherence to current version of ISO 14155 and applicable FDA and local regulations and laws

If a monitor becomes aware that an investigator is not complying with the requirements mentioned above, the monitor is obliged to notify BIOTRONIK study management. BIOTRONIK will evaluate the non-compliance and issue corrective actions, discontinue enrollment or as a last measure close the clinical investigation site.

A monitoring plan will be prepared as additional document. It provides detailed information about frequency and extent of monitoring.

11 STATISTICAL CONSIDERATIONS

11.1 Statistical design, method and analytical procedures

Standard summary statistics will be calculated for all patients and study outcome variables. Categorical data will be summarized via distributions of absolute and relative frequencies. For all relevant parameters 95% confidence intervals will be calculated.

For the analysis of the primary endpoint and the secondary endpoint the Kaplan-Meier plots will be generated and the estimated survival functions of the study groups tested with the two-sided log-rank test. Dependence of survival on major baseline predictors will be studied with proportional hazard Cox models. Hazard ratios and relative 95% confidence intervals for each predictor will be calculated, respectively. Data will be censored at the date of last patient contact. The ITT principle will be applied.

Statistical calculations will be carried out by using STATA 11.1 ®, SAS 9.3 © or R.

11.2 Sample size calculation

The study sample size calculation is based on the minimum relative difference in the 2-year incidence of syncopal recurrences as compared with placebo (pacemaker OFF).

The 2-year incidence of the primary endpoint in the control group will be assumed equal to the incidence observed in the control arm of the ISSUE 3 trial:⁽¹⁶⁾ this was reported as high as 57%. The ISSUE 3 trial was considered as it selected a large population, had very similar inclusion/exclusion criteria, was recently published.

The BIOSync CLS study is designed to detect a 40% relative reduction of the 2-years incidence of syncopal recurrences (from 57% to 34%) with a statistical Type I and II errors of 0.05 (bilateral) and 0.20, respectively.

Further assumptions:

- Exponential distribution of times to first recurrence
- Accrual time: 2 years
- Total study time: 4 years
- Randomization ratio: 1:1
- Loss incidence: 10% (both arms)

With these assumptions a sample size of 62 patients per study arm (124 in total) is required. This estimate must be further increased by 2%, due to the slight power loss induced by the interim analyses (see section 11.6).

In summary, 128 subjects (64 per study arm) are necessary to reach the study primary objective with the required power.

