8.3.2 Blinding

Patients will be blinded to the treatment assignment until the end of the study or the first endpoint event.

Investigators will not be blinded to the randomizations but they will not assess the primary endpoint events.

The primary endpoint events will be collected by dedicated patients' self-administered structured questionnaire. Responses to the questionnaire will determine whether or not the event description and the associated symptoms are consistent with a primary endpoint event.

Questionnaires will be anonymous, identified by the patient ID study code, and provided to patients at enrolment. Questionnaires will be prepared upfront in 8 pre-paid envelopes (additional backup questionnaires may be provided) addressed to an external contract research organization (CRO), whose personnel will remain blinded both to patients' identity and randomization assignment.

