8.8.7 Timelines

The study is planned to start in the second quarter of 2015 and will be probably completed in 2019. The enrolment period is expected to last 24 months and the planned duration of subject's participation is 2 years.

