11.2.1 Required number of primary endpoint events

The required number of primary endpoint events is 62, as calculated with the formula:

$$events = \frac{(z_{\alpha/2} + z_{\beta})^2}{0.25 \log(HR)}$$

where $z_{\alpha/2}$ and z_{β} are the standard normal percentiles ($\alpha=0.05$, $\beta=0.20$), HR is the expected hazard ratio. A HR of about 0.49 was calculated assuming an exponential model of the survival functions with proportional hazard rates.

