11.3 Level of significance and the power of the study

Target study power: 80%

Significance level: 0.05 (bilateral)

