11.6 Provision for interim analyses

Interim analyses will be performed at $t = 0.4$ and 0.7 of the required primary endpoint events or, equivalently, after 25 and 43 endpoint events will be collected.

The final analysis will be performed after the study database has been closed out.

In order to keep the overall type I error at the level of 0.05, two-sided, symmetric O'Brien-Fleming boundaries generated with the Lan-DeMets spending function approach to group-sequential testing will be assumed as early stopping rules for efficacy.

| | | | |
|---------------------|---------|---------|---------|
| t | 0.40 | 0.70 | 1.00 |
| No. endpoint events | 25 | 43 | 62 |
| Z_{up} | 3.3569 | 2.4445 | 2.0005 |
| Z_{low} | -3.3569 | -2.4445 | -2.0005 |
| p | 0.0008 | 0.015 | 0.05 |

Sequential boundaries using the Lan-DeMets method

[figure not shown]

Figure 2. Sequential boundaries during interim analyses. R Software version 3.1.0 (2014-04-10).

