11.7 Termination criteria

With a **sequential study design** the study will stop when a total of 62 primary endpoint events will be collected by the independent agency. The following stopping rules will be used.

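### The sample size counts follow-up beyond 24 months that the trial does not have: 128 patients give about 56–58 events and 73–76% power, not 62 and 80%, and no rule covers the shortfall.

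*Protocol*

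**What the plan says.** **Sizing.** Protocol 11.2 and SAP section 4 assume 2-year incidences of 57% (control) and 34% (CLS), exponential times, 2 years' accrual, 4 years' total study time, 1:1 allocation and 10% loss in both arms. The time basis of the loss is not given. The result is: "With these assumptions a sample size of 62 patients per study arm (124 in total) is required". A 2% increase for the interim looks brings this to 128. Protocol 11.2.1 adds: "The required number of primary endpoint events is 62, as calculated with the formula". Protocol 11.3 states 80% power at two-sided 0.05.

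**Follow-up.** Protocol 8.8.6: "Patients will terminate their study participation at the 24-month in-hospital follow-up or at the assessment of a primary endpoint event occurrence, whichever comes first". Protocol 8.8.7: "The enrolment period is expected to last 24 months and the planned duration of subject's participation is 2 years". Protocol 8.3.2 agrees: "Questionnaires will be prepared upfront in 8 pre-paid envelopes", one per quarter, although backups may be supplied. Protocol 8.6 plans no replacement of subjects.

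**End of study.** Under Protocol 11.7, "the study will stop when a total of 62 primary endpoint events will be collected by the independent agency". Protocol 11.7.1, item 5, directs that after an interim look that does not meet the objective the study goes on to 62 events. Protocol 11.6 says: "The final analysis will be performed after the study database has been closed out". The boundary tables in Protocol 11.6 and SAP 7.6 cover 25, 43 and 62 events only.

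**The concern.** A 4-year calendar does not conflict with 24 months per patient: 2 years' accrual plus 2 years for the last patient makes 4. The difficulty is the sample size drawn from it. If the calculation credited early enrollees with up to 4 years at risk, it counted events that the trial will not observe.

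Two things would follow. The stated power and event count would not belong to the trial as designed. And if neither interim look stopped the study, the instruction to continue to 62 events could usually not be carried out, because nobody would remain under observation. The plan would then be silent on when to analyse and against which boundary. Under Protocol 11.7.1 the coordinating investigator receives the event total monthly, and interim results go to the coordinating investigator and the sponsor. The gap would therefore be filled by people who know the count.

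**Working it through.** **Inputs** (Protocol 11.2, 11.2.1, 11.6): incidences 57% and 34% at 2 years; 64 per arm; alpha 0.05 two-sided; power 80%; final boundary Z = 2.0005.

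**1. Reproduce the plan's figures.**
- Hazards: control −ln(0.43)/2 = 0.422 per year; CLS −ln(0.66)/2 = 0.208 per year. HR = 0.492.
- Events (Schoenfeld): (1.96 + 0.84)² / (0.25 × [ln HR]²) = 7.849 / (0.25 × 0.502) = 62.5; with HR = 0.49, 61.7. The stated 62 is reproduced. The printed formula omits the square on log(HR) and taken literally gives about −44, so this is only a misprint.
- Patients, if all are followed to a common 4-year end: Freedman 123.9 (34%, 10% loss over 2 years); Lachin–Foulkes 123.8 (34.2%, which is exactly a 40% reduction, same loss); Schoenfeld 121.7–123.9 (10% loss per year). The stated 124 is reproduced, and 62 × 1.02 = 63.2, rounded up to 64 per arm.
- Patients, if each is limited to 24 months: Schoenfeld 137–156, Freedman 149–166, Lachin–Foulkes 147–164. None gives 124.

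**2. Expected events with the 24-month limit.** With loss hazard g, events = 64 × Σ over arms of λ/(λ+g) × [1 − exp(−2(λ+g))]. With no loss this is 64 × (0.57 + 0.34) = 58.2.

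**3. Power at the final boundary** (Schoenfeld): Φ(|ln HR| × √(events/4) − 2.0005). With no loss: Φ(0.7086 × √14.56 − 2.0005) = Φ(0.703) = 75.9%.

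The simulation columns use 20,000 log-rank trials per setting, uniform accrual over 2 years, looks at 25 and 43 events, a final analysis at 62 events or at the end of follow-up, and the plan's boundaries. The chance of at least 62 events comes from convolving the two binomials and ignores early stopping.

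| Loss reading | Events, 24 months | Events, common 4-year end | Power, formula | Power, simulated | P(≥62 events) | Stops early (simulated) | Final with <62 events (simulated) |
|---|---|---|---|---|---|---|---|
| none | 58.2 | 74.9 | 75.9% | 75.4% | 28% | 43.8% | 39.7% |
| 10% over 2 years | 55.6 | 70.1 | 73.9% | 73.2% | 14% | 42.8% | 48.4% |
| 10% per year | 53.1 | 65.8 | 72.0% | 70.8% | 6% | 41.8% | 54.3% |

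**4. How often the rule fails.** Among trials that reach a final analysis, the share with fewer than 62 events is 39.7/56.2 = 71%, 48.4/57.2 = 85% and 54.3/58.2 = 93%. Without the 24-month limit, 0.3–3% of trials fall short under the first two loss readings and about 11.5% under the third.

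**5. Visit window.** If every patient used the full +30 days at month 24, events rise only to 59.9 (no loss) or 57.1 (10% over 2 years).

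**6. What is due to the limit.** At exactly 62 events, power at Z = 2.0005 is already 78.5%. The limit itself costs 78.5 − 75.9 = 2.6 points with no loss, 78.5 − 73.9 = 4.6 with 10% over 2 years, and 78.5 − 72.0 = 6.5 with 10% per year.

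**7. Type I error.** Applying Z = 2.0005 at 56–58 events gives an overall two-sided alpha of 0.0488–0.0493. Respending at the actual count gives Z of about 1.988 at 56 events and 1.993 at 58.

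**The case against.** No sentence says that anyone is followed beyond 24 months. The flaw is inferred by back-calculation, and neither the formula nor the loss period is stated. That is fair, and the inference should be described as such. It is nevertheless a firm one: every log-rank method tried needs at least 137 patients under the limit, and no loss reading brings 128 patients to 62 expected events.

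The power loss is modest. The limit accounts for about 3–5 points, the shortfall of 4–6 events is about one standard deviation of the event count, and the 57% control rate is itself borrowed from another trial. This stands as to size. It does not make the stated 80% correct.

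Database close-out (Protocol 11.6) already triggers a final analysis, last-patient-out is fixed by enrolment, and Lan–DeMets spending allows a different final event count. This stands in part: close-out is the natural step, and validity is not threatened. But close-out is not tied to the last 24-month visit, it conflicts with the instruction to continue to 62 events, and neither document says to recompute the boundary.

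The eight envelopes are weak evidence, since backups are allowed. Agreed; Protocol 8.8.6 and 8.8.7 carry the point without them.

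**Conclusion.** The concern holds. Under the trial's own 24-month limit, 128 patients are expected to give about 56–58 events (53 if loss is 10% per year). Power for 57% versus 34% is about 73–76% (71–72% at 10% loss per year), not 80%. The target of 62 events will more often than not be missed in trials that pass both interim looks, and the documents give no rule for that case.

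The figures rest on the plan's own incidences, exponential times and proportional hazards. The unstated loss period moves them but does not change the conclusion. The test, the estimate and the type I error are not compromised. The faults are an overstated power and an end-of-study rule that usually cannot be carried out, and both should be corrected.

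**What to change.** **Protocol 11.2, 11.2.1 and 11.3, and SAP section 4.** Redo the calculation with 24 months per patient, name the formula and state the loss period. Report the resulting events and power: about 56–58 and 73–76% for 57% versus 34% if loss is at most 10% over 2 years. At 64 per arm, 80% power corresponds to a CLS incidence of about 32.4–32.9%. Alternatively, the participation limit and the follow-up implied by the calculation must be reconciled in some other way. For information, 80% power for 57% versus 34% under the limit needs about 71–77 per arm with all events analysed (about 80 at 10% loss per year).

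**Protocol 11.7 and 11.7.1 item 5, and SAP 7.6.** Add wording such as: *The final analysis takes place at 62 primary endpoint events or when the last patient completes 24 months, whichever is first; the final Lan–DeMets boundary is recomputed at the observed number of events.* Align the close-out sentence in Protocol 11.6 with this.

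**Minor.** Print the event formula with log(HR) squared.

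**Cost.** Wording in two documents and a less favourable stated power. No extra patients are needed unless the sponsor chooses to keep 80% for 57% versus 34%.
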